Statistical Considerations	
Based on a standard 3+3 design, up to approximately six patients may be enrolled in each dose level cohort evaluated during the dose escalation portion of the study; a minimum of nine and a maximum of 18 patients who complete the safety review period is anticipated.
 
The sample size for the dose level expansion cohorts is selected to obtain a reasonable estimate of clinical benefit, defined for this study as response rate defined by RECIST v1.1 criteria, to be used for planning future studies. A Simon two-stage design will be used for each dose cohort; in the Simon two-stage design and assuming a baseline overall response rate of 10% with doxorubicin monotherapy and an alternative of 25%, a power of 90% and one-sided Type 1 error set at 0.20, each dose level cohort will require 18 patients enrolled and evaluable for response in Stage 1. With at least two clinical responses, an additional 13 patients will be enrolled in Stage 2. The combination will be considered worthy of further study if at least five clinical responses observed in either 31-patient cohort.

Dose Delays, Dose Modifications, Guidelines for Treatment Discontinuation and Study Withdrawal	
Patients who enter the study with symptoms or laboratory values equivalent to NCI CTCAE Grade 1 or Grade 2 should not have dose reductions related to the persistence or mild worsening of those symptoms or laboratory values.
 
Dose reductions may be warranted if worsening of symptoms or laboratory values is clinically significant in the opinion of the Investigator and in the case of unacceptable treatment-related adverse events. Recognizing that it may be difficult to make attribution to one agent or the other in the combination regimen and in collaboration with the Sponsor Medical Monitor, best efforts should be made to consider the underlying reason for the worsening of symptoms or development of a treatment-related adverse event so that dosing of the appropriate study drug can be modified.
 
Except in the case of proteinuria, asymptomatic laboratory abnormalities should not result in dose interruptions, modifications, or discontinuation of study therapy unless determined by the Investigator to be clinically significant or life-threatening.

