	
The Investigator should withdraw a patient from all study-related treatment for any of the following reasons:
 

• An unacceptable adverse event or safety observation, such as a persistent moderate toxicity that is intolerable to the patient, that is in the opinion of the Investigator clearly attributed to TTI-621

• An unacceptable adverse event or safety observation, such as a persistent moderate toxicity that is intolerable to the patient, that is in the opinion of the Investigator clearly attributed to doxorubicin and the patient has received fewer than four cycles of doxorubicin. A patient who has completed four cycles of doxorubicin treatment and experiences an adverse event that requires discontinuation of doxorubicin treatment despite optimal prophylaxis and supportive care and is receiving clinical benefit may be eligible to continue to TTI-621 monotherapy with the next cycle (Cycle 5 or Cycle 6) after discussion with the Sponsor Medical Monitor and provided the patient has not experienced disease progression and TTI-621 re-treatment guidelines as described in Section 9.2.2 are met; the patient may be replaced or an additional patient may be enrolled for the purposes of having a heterogeneous population for evaluation of safety and clinical activity as described in Section 6.7.

• Any event which would cause TTI-621 or doxorubicin to be modified by more than two dose reductions or to be held for more than 42 days from the last administered dose and is not attributable to a particular agent of the combination regimen; exception is made for patients who are receiving meaningful clinical benefit and the investigator feels, with Sponsor Medical Monitor concurrence, that continued treatment is in the best interest of the patient

• Any treatment-related adverse event that is deemed life-threatening, regardless of grade; exception is made for patients in whom the life-threatening adverse event is attributed to doxorubicin and has occurred despite optimal prophylaxis and medical support and the patient is receiving clinical benefit and has received at least four cycles of doxorubicin treatment and the investigator feels, with Sponsor Medical Monitor concurrence, that continuation with TTI-621 monotherapy would be reasonable; the patient may be replaced or an additional patient enrolled for the purposes of having a heterogeneous population for evaluation of safety and clinical activity as described in Section 6.7.

• Documentation of objective (radiographic) disease progression; for patients with asymptomatic progression and in the absence of unacceptable toxicity, the patient should continue treatment and a confirmation scan should be

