## 9.5. Guidelines for Management of Thrombocytopenia Assessed as Related to Study Treatment (TTI-621 and/or Doxorubicin)

Guidelines for management of treatment-emergent thrombocytopenia occurring in Cycles 1 – 6 or any cycle when doxorubicin and TTI-621 are administered together are provided in [Table 22](#). Guidelines for management of treatment-emergent thrombocytopenia occurring in Cycles  $\geq 7$  or when TTI-621 is administered as monotherapy are provided in [Table 23](#).

**Table 22. TTI-621 and Doxorubicin Treatment Guidelines Based on Thrombocytopenia Assessed as Related to Study Treatment in Cycles 1-6 (Combination Treatment)**

Platelet Count on Day 8	Management Guidelines
<LLN – $75 \times 10^9/L$	
 
Continue TTI-621 and doxorubicin at same dose
 

$75 \times 10^9 – 50 \times 10^9/L$	
 
Continue TTI-621 and doxorubicin at same dose
 

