$50 \times 10^9 – 25 \times 10^9/L$	
 
Omit TTI-621 on Day 8
 
Monitor platelet recovery (CBC twice weekly recommended)
 
Consider platelet transfusion per ASCO guidelines if clinically indicated
 
On Day 1 of next cycle: 
 
if platelets have recovered to <math>\geq 75 \times 10^9/L</math>, initiate cycle with doxorubicin at the same dose and TTI-621 at one dose level reduction
 
if platelets have not recovered to <math>\geq 75 \times 10^9/L</math>, hold doxorubicin and TTI-621 and monitor platelets; initiate the cycle when platelets recover to <math>\geq 75 \times 10^9/L</math> with doxorubicin at same dose and TTI-621 at one dose level reduction
 
 
 
In the case of a second occurrence of platelet count decrease to <math><50 \times 10^9</math>, follow the guidelines above or consult with the Sponsor Medical Monitor regarding management
 
The reduced dose of TTI-621 should be used for the remaining combination cycles
 
When the subject completes the combination portion of the study and moves to TTI-621 monotherapy: 
 
the original TTI-621 dose level should be re-instated and platelet counts monitored
 
in the case of platelets <math>< 50 \times 10^9/L</math> without other causality on Day 15, hold TTI-621 until platelets are <math>\geq 50 \times 10^9/L</math> and then continue with TTI-621 at a one dose level reduction
 
on second occurrence of platelets <math>< 50 \times 10^9/L</math> without other causality, reduce TTI-621 by an additional dose level and monitor for tolerability or consult with the sponsor medical monitor regarding management
 
in the absence of disease progression, further dose reductions may be implemented after discussion with the sponsor medical monitor
 
 
 

Platelet Count on Day 8	Management Guidelines

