Any platelet count with clinically-relevant bleeding (more than easily-controlled epistaxis, mild gum bleeding or menses)	
 
• Hold TTI-621 on Day 8
 
• Monitor platelet recovery (CBC twice weekly recommended)
 
• Consider platelet transfusion per ASCO guidelines
 
• On Day 1 of next cycle: 
 
◦ if platelets have recovered to <math>\geq 75 \times 10^9/L</math> and bleeding has resolved, reduce doxorubicin and TTI-621 by one dose level and initiate cycle
 
◦ if platelets have not recovered to <math>\geq 75 \times 10^9/L</math> and/or bleeding has not resolved, hold doxorubicin and TTI-621 and monitor platelets; initiate the cycle when platelets recover to <math>\geq 75 \times 10^9/L</math> with doxorubicin and TTI-621 each at one dose level reduction
 
 
 
• In the case of a second occurrence of platelet count decreased with bleeding attributed to study drug treatment, consult with the sponsor medical monitor regarding management
 
• The reduced dose levels of doxorubicin and TTI-621 should be used for the remaining combination cycles
 
• When the subject completes the combination portion of the study and moves to TTI-621 monotherapy: 
 
◦ the original TTI-621 should be re-instated and platelet counts monitored
 
◦ in the case of platelets <math>< 50 \times 10^9/L</math> on D15, hold TTI-621 until platelets are <math>\geq 50 \times 10^9/L</math> and then continue with TTI-621 at one dose level reduction
 
◦ on Day 1 of the next cycle, if platelet count remains <math>\geq 50 \times 10^9/L</math>, the reduced TTI-621 dose level should be used for the remainder of the subject's participation. If platelet counts do not remain <math>\geq 50 \times 10^9/L</math>, reduce TTI-621 by another dose level and monitor for tolerability.
 
◦ in the absence of disease progression, further dose reductions may be implemented after discussion with the Sponsor Medical Monitor.
 
 
 

**Table 23. TTI-621 Treatment Guidelines based on Thrombocytopenia Assessed as Related to Study Treatment in Cycles  $\geq 7$  (TTI-621 Monotherapy)**

Note that these guidelines are intended to address a patient who has not experienced thrombocytopenia in the combination portion of the study but presents with thrombocytopenia during monotherapy treatment.

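### The Synopsis rule on asymptomatic laboratory abnormalities does not exempt the blood-count rules of Section 9, so the two disagree for some counts, chiefly Day 8 platelets of 25-50 x 10^9/L without bleeding

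*Protocol*

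**What the plan says.** The Synopsis row on dose delays and modifications covers asymptomatic laboratory findings and names proteinuria as the only exception. Such "abnormalities should not result in dose interruptions, modifications, or discontinuation of study therapy unless determined by the Investigator to be clinically significant or life-threatening". Blood counts are not exempted. The same row permits dose reductions "in the case of unacceptable treatment-related adverse events". It also cites Section 9.2.2, but only where a patient who stops doxorubicin after four cycles "may be eligible to continue to TTI-621 monotherapy with the next cycle (Cycle 5 or Cycle 6) after discussion with the Sponsor Medical Monitor".

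Protocol Section 9.5, whose heading begins "Guidelines for Management of Thrombocytopenia Assessed as Related to Study Treatment", sets out Table 22 for the combination cycles. At Day 8 platelets of 50-25 x 10^9/L the first instruction is "Omit TTI-621 on Day 8". The next cycle then starts with TTI-621 one level lower, even if platelets have recovered to at least 75 x 10^9/L, and doxorubicin stays at the same dose. The row adds: "The reduced dose of TTI-621 should be used for the remaining combination cycles". At the move to monotherapy, "the original TTI-621 dose level should be re-instated and platelet counts monitored". Bleeding has its own row, "Any platelet count with clinically-relevant bleeding", so the 25-50 row reaches patients without it.

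Section 9.2.2 refers the reader to Tables 12-15 and 21-23 for intra-cycle dosing, delays and modifications after specific adverse events.

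**The concern.** The two texts use different tests. The Synopsis asks whether the Investigator finds the abnormality clinically significant or life-threatening. Table 22 asks whether the thrombocytopenia is treatment-related and how low the count is. A related, symptomless count that the Investigator considers unimportant fails the first test and meets the second. That judgment is plausible: Section 3.8.1 describes the thrombocytopenia seen with TTI-621 as transient and reports no increased bleeding or other clinical sequelae.

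Read literally, the Synopsis then permits a TTI-621 dose on a day when the platelet safety table withholds it. Two sites could treat the same count differently and each cite protocol text. Treatment delays and discontinuations are part of the safety endpoints (Protocol 4.2 and 4.4), SAP 9.1 summarizes reductions, held infusions and cycle delays, and SAP 7.3 has the clinical team class deviations as major or minor. All of these depend on knowing which instruction applied.

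**Working it through.** **Step 1. Which Section 9 rules conflict?** A rule conflicts only if it can apply to a patient without symptoms, lacks the Investigator test, and concerns a value that is not already life-threatening.

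| Rule | Action | In conflict? |
|---|---|---|
| Table 22, Day 8 platelets 50-75 x 10^9/L | Continue | No; both texts agree |
| Table 22, Day 8 platelets 25-50, no bleeding | Omit, then one level lower | Yes |
| Table 22, Day 8 platelets below 25 | Omit, then reduce both drugs | Probably not |
| Table 23, Day 15 platelets 25-50, no bleeding | Hold, then one level lower | Yes |
| Tables 9 and 16, Section 9.3.3.4, ANC delay row of Table 19 (cycle-start ANC below 1 or platelets below 75 x 10^9/L) | Delay the cycle | Yes |
| Table 13, Grade 3 anemia | Delay; reduce if the delay exceeds one week or the event recurs | Yes |
| Table 21, Grade 3 neutropenia or anemia | Delay and reduce both drugs | Yes |
| Table 13, neutropenia rows | Delay, with or without reduction | No; Grade 4, febrile or infected |
| Table 19, remaining rows | Reduce, or Investigator's discretion | No; fever, infection or Grade 4, and one row already leaves the choice to the Investigator |

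The entry below 25 x 10^9/L assumes that this count is Grade 4. The documents give no platelet cut-offs for grades, but SAP 9.3 labels Grade 4 life-threatening, which would meet the Synopsis exception. The same label removes the Grade 4 neutropenia rows.

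Section 9 does use the Investigator's significance judgment for non-hematologic laboratory findings (Tables 14 and 21). Its absence from the hematologic rows suggests that those were meant to apply without it.

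**Step 2. One patient under each text.** Take Day 8 platelets of 40 x 10^9/L, treatment-related, no bleeding, judged not clinically significant. Synopsis: give the Day 8 dose and keep the level. Table 22 with Table 10: omit the dose, then go from 2.0 to 1.4 mg/kg, or from 1.0 to 0.7 mg/kg. From 0.2 mg/kg, Table 10 gives discontinuation, which Section 5.3 lists as a stopping criterion, although Section 9.2.3 allows a lower dose after consulting the Medical Monitor. No cumulative figure applies at 0.2 mg/kg.

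**Step 3. Size for one event.** TTI-621 is given on Days 1 and 8 of six cycles, so 12 doses are planned. Assume one event, on Day 8 of Cycle k, no recurrence, and all six cycles completed. Table 22 gives 2k-1 full doses, 1 omitted dose and 2(6-k) reduced doses.

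- At 2.0 mg/kg: 2.0(2k-1) + 1.4 x 2(6-k) = 14.8 + 1.2k, against 12 x 2.0 = 24 mg/kg.
- At 1.0 mg/kg: 1.0(2k-1) + 0.7 x 2(6-k) = 7.4 + 0.6k, against 12 mg/kg.

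| Cycle of event | 1 | 2 | 3 | 4 | 5 | 6 |
|---|---|---|---|---|---|---|
| Total at 2.0 mg/kg | 16.0 | 17.2 | 18.4 | 19.6 | 20.8 | 22.0 |
| Total at 1.0 mg/kg | 8.0 | 8.6 | 9.2 | 9.8 | 10.4 | 11.0 |
| Below the unchanged plan | 33.3% | 28.3% | 23.3% | 18.3% | 13.3% | 8.3% |

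If only the omission is in dispute, the difference is 1/12 = 8.3% in any cycle. Because the original level returns at monotherapy, the calculated difference is confined to Cycles 1-6.

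**The case against.** The best answer is that a general sentence in a summary should yield to a specific, counted rule in the body. Section 9.2.2 sends intra-cycle dosing to the tables without restriction, and Section 9.5 is devoted to thrombocytopenia. A careful site would probably follow Table 22. That stands as the better reading, but it has to be inferred. Section 9.2.2 claims no precedence over the Synopsis, and the Synopsis cites it only for early monotherapy.

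Second, the Investigator may simply call 25-50 x 10^9/L clinically significant, and the conflict then disappears. If that range is Grade 3 (an assumption of the same kind as above), the generic description of Grade 3 in Protocol 13.4 points that way. But those descriptions are for terms not listed in CTCAE, and the Synopsis leaves the decision to the Investigator. The conflict therefore arises only where the judgment is negative.

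Third, the allowance for unacceptable treatment-related events may cover the reduction. This is fair, and it is why the lower figure is 1 of 12 doses. The allowance names reductions, not omitting a dose.

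A reader might go further and infer that sites dosed under the Synopsis and so contributed to the Day 8 Grade 3 or 4 thrombocytopenia that closed Cohort B (SAP 4.3.2). Nothing in the SAP says so. The percentages are differences between two readings for one hypothetical patient, not observed exposure. Nor is every hematologic rule in Section 9 contradicted, as Step 1 shows.

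**Conclusion.** The inconsistency is real but narrow. It arises only when the Investigator judges one of the counts or grades marked in Step 1 not clinically significant. Day 8 platelets of 25-50 x 10^9/L are the clearest case because there the Synopsis allows a dose that the platelet table withholds.

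Per event the size is 8%, or 8-33% at 2.0 or 1.0 mg/kg if the reduction is also disputed, under the assumptions of Step 3. The number of patients affected is unknown, and no site is shown to have departed from Table 22. SAP 4.3.2 cites a letter (PACL No 5) that is not among these documents and may already have clarified the point. The Simon design's sample size and error rates do not change, and SAP 6.7.1 keeps dose-reduced patients in their initially planned dose cohort for safety.

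This is a minor wording correction to safety text, not a question of design. The SAP describes enrollment into Cohort B Stage 1 and Cohort C as done, so the benefit is mainly for patients still on treatment and for consistent classing of deviations.

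**What to change.** At the next amendment, add *except as specified in Section 9* to the Synopsis sentence, so that the count- and grade-based tables govern. Tell sites the same by clarification letter now, unless an existing letter already does. The change is one clause. Its cost is the amendment process in Protocol 14.9: sponsor approval, Investigator agreement, IRB approval before implementation, and regulatory submission. No analysis needs to change.

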## STUDY SCHEMA SUMMARY

In the dose escalation portion of the study, eligible patients with high-grade leiomyosarcoma, undifferentiated pleomorphic sarcoma, myxofibrosarcoma, dedifferentiated liposarcoma, angiosarcoma or epithelioid sarcoma will receive doxorubicin at 75 mg/m^2 and escalating doses of TTI-621 in a standard 3+3 design. For the expansion portion of the study, a low dose (Cohort A) and a high dose (Cohort B) of TTI-621 will be selected for evaluation with 75 mg/m^2 doxorubicin in patients with high-grade leiomyosarcoma using a Simon two-stage design. Due to cumulative toxicity that limits its use, doxorubicin is administered on Day 1 of 21-day cycles for a maximum of six cycles (18 weeks). In Cycle 1 through Cycle 6, TTI-621 will be administered on Day 1 and Day 8 of each 21-day cycle. Beginning with Cycle 7, TTI-621 will be administered as monotherapy on Days 1 and 15 of 28-day cycles.

During the dose escalation portion of the study, eligible patients will be enrolled to the cohort that is open at the time they present to the study. Based on known safety of the lowest planned dose of TTI-621, 0.2 mg/kg, gleaned from other clinical trials, it is anticipated that this dose will serve as the TTI-621 dose level for Cohort A. Thus, expansion Cohort A will open to enrollment once that dose level is judged to be safe in the dose escalation portion of the study. If a dose escalation cohort and expansion Cohort A are open to enrollment at the same time, priority for enrollment will be given to the dose escalation cohort and enrollment into expansion Cohort A will be limited to those patients who present to the study after enrollment to a dose escalation cohort is closed and meet all the eligibility criteria for the expansion portion of the study (including documentation of the leiomyosarcoma indication).

When both expansion cohorts are open to enrollment, cohort assignment will be made on an alternating basis, with assignment made by the CRO overseeing the study on behalf of the sponsor independent of investigator input and based strictly on chronology of verification of eligibility of patients as they complete screening assessments.

In the Simon two-stage design and assuming a baseline ORR of 10% with doxorubicin monotherapy and an alternative of 25%, a power of 90% and one-sided Type 1 error set at 0.20, each dose level cohort will require 18 patients enrolled and evaluable for response in Stage 1; with at least 2 clinical responses, an additional 13 patients will be enrolled in Stage 2. The combination will be considered worthy of further study if at least five clinical responses are observed in either 31-patient cohort.

## ABBREVIATIONS

ABCL	aggressive B-cell lymphoma
CCI	
AE	adverse event
AESI	adverse event of special interest
ALL	acute lymphoblastic leukemia
ALT	alanine aminotransferase
AML	acute myeloid leukemia
ANC	absolute neutrophil count
AST	aspartate aminotransferase
AUC	area under the curve
BUN	blood urea nitrogen
CLL	chronic lymphocytic leukemia
C max	maximum blood concentration
CNS	central nervous system
CR	complete response
CRO	contract research organization
CT	computed tomography
CTCAE	Common Terminology Criteria for Adverse Events
CTCL	cutaneous T-cell lymphoma
D	Day
DCR	disease control rate
DILI	Drug Induced Liver Injury
DLBCL	diffuse large B-cell lymphoma
DLT	dose-limiting toxicity
DOR	duration of response
EC 50	effective half-maximal concentration
ECG	electrocardiogram
ECOG	Eastern Cooperative Oncology Group
eCRF	electronic case report form
EDB	exposure during breastfeeding
EDC	electronic data capture
EDP	exposure during pregnancy
eGFR	estimated glomerular filtration rate
CCI	
EOI	End of Infusion
EORTC	European Organisation for Research and Treatment of Cancer
FDA	Food and Drug Administration
FFPE	fresh-fixed paraffin embedded
G-CSF	granulocyte colony-stimulating factor
GCP	Good Clinical Practice
GLP	Good Laboratory Practice
GM-CSF	granulocyte-macrophage colony-stimulating factor
HCl	Hydrochloride
HIPAA	Health Information Portability and Accountability Act
HL	Hodgkin lymphoma

IBCL	indolent B-cell lymphoma
ICF	informed consent form
ICH	International Council for Harmonisation
IEC	Independent Ethics Committee
IgG1	immunoglobulin G1
INR	International Normalized Ratio
IRB	Institutional Review Board
IRR	infusion-related reaction
CCI	
IV	intravenous(ly)
LDH	lactate dehydrogenase
LVEF	left ventricular ejection fraction
MDS	myelodysplastic syndromes
MedDRA	Medical Dictionary for Regulatory Activities
MF	mycosis fungoides
MHC	major histocompatibility complex
MRI	magnetic resonance imaging
MTD	maximum tolerated dose
NA	not available
NBF	neutral-buffered formalin
NCI	National Cancer Institute
NE	not evaluable
NGS	next-generation sequencing
NHL	non-Hodgkin lymphoma
NSAID	nonsteroidal anti-inflammatory drug
ORR	overall response rate
OS	overall survival
P-gp	P-glycoprotein
PD	pharmacodynamics; progressive disease
PD-1	programmed death-1
PD-L1	programmed death-ligand-1
PET	positron emission tomography
PFS	progression-free survival
PK	pharmacokinetics
PR	partial response
PS	performance status
PSSA	Pfizer SAE Submission Assistant
PTCL	peripheral T-cell lymphoma
QLQ-C30	Quality-of-Life Questionnaire Core 30
QoL	quality of life
RBC	red blood cell
RECIST	Response Evaluation Criteria in Solid Tumours
SAE	serious adverse event
SARS-CoV-2	severe acute respiratory syndrome coronavirus 2
SAP	Statistical Analysis Plan
SD	stable disease
SIRP $\alpha$	signal regulatory protein alpha

SMPC	Summary of Product Characteristics
SRSD	Single Reference Safety Document
SUSAR	suspected unexpected serious adverse reactions
$t_{1/2}$	terminal half-life
TAM	tumor-associated macrophage
TCL	T-cell lymphoma
CCI	
THC/CBD	tetrahydrocannabinol/cannabidiol
TEAE	treatment-emergent adverse event
$T_{max}$	time to $C_{max}$
T-Vec	talimogene laherparepvec
ULN	upper limit of normal
US	United States
USP	United States Pharmacopeia
USPI	United States Product Insert
WBC	white blood cell
WOCBP	woman of child-bearing potential

